5.15. Important Protocol Deviations

Important protocol deviations that potentially compromise the data integrity and patients' safety will be listed. These deviations will include those defined by:

- Informed consent
- Inclusion/Exclusion Criteria
- Investigational Product
- Study Procedures
- Administrative/Oversight
- Safety
- Other

Based on the discussion with study team, the detailed description of each deviation within the above category and the method to identify each deviation will be documented.

5.16. Interim Analyses and Data Monitoring

For each cohort, one interim analysis of futility will be conducted after the 29th patient in the cohort has completed Cycle 3, and, if required, the response is confirmed. The interim analysis will be conducted to assess whether the respective cohort is unlikely to achieve statistical significance on its primary endpoint and may also include PK data in order to confirm that patients are in the expected systemic exposure range.

5.17. Planned Exploratory Analyses

5.17.1. Biomarker Analyses

Descriptive summaries and statistical analyses results will be provided to support the biomarker research objectives outlined in the protocol.

For biomarkers obtained from whole-blood samples, descriptive statistics will be reported at pre-treatment (baseline), post-treatment and post-regression time points. Each biomarker will be described using summary statistics at the study, cohort, and at the level of other patient subgrouping of interest. Any correlations or associations between the biomarkers measured on the same patient will also be looked at.

For biomarkers obtained from biopsies done on lesions, descriptive statistics will be reported at pre-treatment (baseline), post-treatment and post-regression time points as described in the paragraph above. In addition, descriptive statistics on lesions that regressed after treatment will be provided. Provided a sufficient number of patients with such biopsies are available, additional

analyses may be undertaken to investigate the correlation between the change in the status/level of the biomarker and the change in the size of the lesion.

All biomarkers deemed relevant may be specifically investigated with the aim of understanding the biomarker profile of patients who receive the greatest clinical benefit from LY2606368. These investigations will look at the correlation/association between the baseline (archival or pre-treatment) status/level of the biomarker(s) and measures of clinical benefit such as objective clinical response status (CR/PR or no-CR/PR) or disease control status (CR/PR/SD or no-CR/PR/SD). Where a change in the status/level of a biomarker over time can be ascertained, additional exploratory analyses may be undertaken to assess the effect of the change or its magnitude on the same clinical efficacy endpoints. For secondary efficacy measures of PFS and OS, parametric and semi-parametric survival analysis will be undertaken to quantify the association between the biomarker status and the time-to-event efficacy measure.

For serially measured plasma-based biomarkers, change from baseline to subsequent time points may be associated with clinical response outcomes. In addition, the time-course relationship of these biomarkers with safety and/or PK parameters (systemic exposure) may also be investigated.

Biomarker results may also be analyzed to elucidate the associations between the baseline status/level, or change in status/level and including, but not limited to, the mechanism of action of LY2606368, sensitivity to CHK1 inhibition, and sensitivity or resistance to platinum-based therapies.

5.17.2. Correlation between Change in Tumor Size and Efficacy Measures

Change in tumor size (CTS) will be assessed in each patient using radiographic imaging. This endpoint will be based on tumor measurements collected by the centers according to RECIST 1.1. Tumor size is the sum of the tumor measurements for target lesions at each tumor evaluation. Change in tumor size is defined as the percent change in tumor size from the baseline evaluation to the evaluation at the end of Cycle 3.

$$\text{CTS} = (\text{tumor size at Cycle 3} - \text{tumor size at baseline}) / (\text{tumor size at baseline})$$

The correlation between CTS and PFS will be tested using the Spearman's correlation coefficient.

Additional exploratory analyses of the data will be conducted as deemed appropriate.

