	Plasma biomarker sample	X				X		Collect prior to dosing on Day 1 of Cycles 1 and 3 only.
	ECG	X		X		X		Single local ECG collected at each time point. Day 1: predose, 10 min after EOI (±5 min), 30 min after EOI (±10 min), and >1 hour after EOI. Cycle 2-X: predose. However, if QTcF >480 msec is observed on Day 1, then 10 min after EOI (±5 min), 30 min after EOI (±10 min), and >1 hour after EOI should also be collected in subsequent cycles.
Optional Tumor Biopsy			X				Can occur at any time during patient's treatment.	

Study Period		Study Treatment Period						
		1		2		3-n ^a		
Cycle/Visit		14 days		14 days		14 days		
Duration		14 days		14 days		14 days		
Relative Day within Dosing Cycle		1	8	1	8	1	8	
Tumor Assessment	Radiologic imaging according to RECIST 1.1						X	For the first 52 weeks following enrollment, perform approximately every 6 weeks starting at the end of Cycle 3 (eg, Days 8-14). Thereafter, perform approximately every 12 weeks. The scanning interval (6 or 12 weeks [± 1 week]) should be maintained even if cycles are delayed. As a result, after Cycle 3, the scans may not always occur at the end of a cycle. The same method of imaging used at baseline should be used for each subsequent assessment. Scans should also be obtained as clinically indicated.
Tumor Assessment	Tumor measurement (palpable or visible)						X	Perform at least every 6 weeks starting in Cycle 3 on the same day as the radiologic imaging.
Adverse Events Collection/ CTCAE Grading		X		X		X		
Concomitant Medication Notation		X		X		X		
Lung Cancer Symptom Scale		X		X		X		The LCSS is to be administered prior to extensive interaction with site personnel and prior to administration of study drug.
Study Treatment	LY2606368	X		X		X		IV over approximately 60 (+10) min

Abbreviations: BSA = body surface area; CT = computed tomography; CTCAE = Common Terminology Criteria for Adverse Events (NCI 2009); ECG = electrocardiogram; ECOG = Eastern Cooperative Oncology Group (Oken et al. 1982); EOI = end of infusion; IV = intravenous; min = minute; LCSS = Lung Cancer Symptom Scale; PK = pharmacokinetic; QTcF = QT interval using Fridericia’s correction; RECIST 1.1 = Response Criteria In Solid Tumors Version 1.1 (Eisenhauer et al. 2009).

Table JTJH.2.3. Post-Treatment Follow-Up Schedule of Activities

Study Period		Post-discontinuation Follow-Up		
		Short-term Follow-Up	Long-term Follow-Up	
Duration		30 ± 5 days	60 ± 14 days	
Visit		801	802-X	

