Relative day within a cycle		Period begins the day after stopping of study treatment and lasts approximately 30 days	Period begins 1 day after short-term follow-up period is completed and continues until death, study withdrawal, or the patient is lost to follow-up	
Procedure Category	Procedure			Comments
Physical Examination	Physical examination (including weight)	X		
	Vital signs	X		Includes blood pressure, pulse, and temperature.
	ECOG performance status	X		
Tumor Assessment	Radiologic imaging according to RECIST 1.1	X		The same method of imaging (CT scan, spiral CT, etc.) used at baseline should be used for each subsequent assessment. Not required if progressive disease is documented while on treatment or if there are clear signs of clinical progression.
	Tumor measurement (palpable or visible)	X		Performed at the same time as radiologic imaging.
Adverse Events Collection/CTCAE Grading		X	X	After Visit 801, only study treatment-related serious events are reported.
Concomitant Medication Notation		X		
Lab/Diagnostic Tests	Hematology	X		
	Chemistry	X		
	ECG	X		
	Exploratory blood sample for biomarkers	X		
	Plasma biomarker sample	X		
	Optional posttreatment biopsy		X	
Health Outcome Measure	Lung Cancer Symptom Scale	X		The LCSS will need to be administered prior to extensive interaction with site personnel.
Follow-Up	Survival Assessment		X	Approximately every 60 (±14) days (telephone assessment is acceptable).

Abbreviations: CT = computed tomography; CTCAE = Common Terminology Criteria for Adverse Events (NCI 2009); ECOG = Eastern Cooperative Oncology Group (Oken et al. 1982); LCSS = Lung Cancer Symptom Scale; RECIST 1.1 = Response Criteria In Solid Tumors Version 1.1 (Eisenhauer et al. 2009).

Table JTJH.2.4. Continued Access Schedule of Activities

	Study Treatment	Follow-Up ^a	
Visit	501-5XX	901	
Procedure ^b			Comments
AE collection	X	X	
Administer LY2606368	X		IV over approximately 60 (+10) minutes once every 14 days.

Abbreviations: AE = adverse event; IV = intravenously.

- a Continued access follow-up begins 1 day after the patient and the investigator agree that the patient will no longer continue treatment in the continued access period and lasts approximately 30 days. No follow-up procedures will be performed for a patient who withdraws informed consent unless he or she has explicitly provided permission and consent.
- b Efficacy assessments will be done at the investigator's discretion based on the standard of care.

3. Introduction

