4.3. Exploratory Objectives

- To explore biomarkers associated with the efficacy and safety of LY2606368, the exposure (PK) of LY2606368, the mechanism of action of CHK1, DNA damage response pathways or downstream effects, cell cycle markers, immune function, or cancer pathobiology
- To explore whether ongoing measurement of tumor shrinkage (such as changes in tumor size) correlate with efficacy measures

5. A Priori Statistical Methods

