5.10.2. Secondary Efficacy Analyses

Secondary efficacy variables are defined as follows:

Disease control rate is defined as the number of patients who achieve a BOR of CR, PR, or stable disease (SD) divided by the total number of patients enrolled to the corresponding cohort (full analysis set). The confirmation of CR and PR is required. The BOR for patients with an unconfirmed PR or CR observation will be classified as SD, as long as they otherwise meet those requirements (see following sentence). In the case of SD, measurements must have met the SD criteria at least once after study entry at a minimum interval (not less than 5 weeks). The DCR, with exact 95% CI, will be summarized for each cohort using the Clopper-Pearson method.

Duration of response is defined as the time from the date measurement criteria for CR or PR (whichever is first recorded) are first met until the first date that disease is recurrent or objective progression is observed, per RECIST 1.1 criteria, or the date of death from any cause in the absence of objectively determined disease progression or recurrence.

Overall survival is defined as the time from enrollment until death from any cause. If the patient is alive or lost to follow-up at the time of data analysis, OS data will be censored on the last date the patient is known to be alive. Overall survival curves, median OS, and OS rates at various time points with 95% CI, for each cohort will be estimated using the Kaplan-Meier method (Kaplan and Meier 1958).

Progression-free survival is defined as the time from enrollment until the first radiographic documentation of progression or death from any cause in the absence of PD. Patients known to be alive and without disease progression will be censored at the time of the last adequate tumor assessment prior to study completion (a detailed PFS event/censoring scheme is provided in [Table JTJH.5.2](#)). Progression-free survival curves, median PFS, and PFS rates at various time points with 95% CI for each cohort will be estimated using the Kaplan-Meier method (Kaplan and Meier 1958).

Table JTJH.5.2. PFS Event/Censoring Scheme

Situation ^a	Event/Censor	Date of Event or Censor
Tumor progression or death	Event	Earliest date of PD or death
No tumor progression and no death	Censored	Date of last adequate radiological assessment or date of enrollment (whichever is later) ^b
Unless		
No baseline radiological tumor assessment available	Censored	Date of enrollment

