No adequate postbaseline radiological tumor assessment available and death reported after 2 scan intervals following enrollment ^{b,c}	Censored	Date of enrollment
Tumor progression or death documented immediately after 2 or more scan intervals following last adequate radiological tumor assessment or enrollment (whichever is later) ^{b,c}	Censored	Date of last adequate radiological assessment or date of enrollment (whichever is later) ^b

Abbreviations: CR = complete response; PD = progressive disease; PFS = progression-free survival; PR = partial response; SD = stable disease.

- a Symptomatic deterioration (that is, symptomatic progression that is not radiologically confirmed) will not be considered as tumor progression.
- b Adequate radiological tumor assessment refers to an assessment with one of the following responses: CR, PR, SD, or PD.
- c For the first 52 weeks following enrollment, radiologic imaging for tumor assessment will be performed approximately every 6 weeks (that is, every 3 cycles) starting at the end of Cycle 3. Thereafter, it will be performed approximately every 12 weeks. The same method of imaging used at baseline should be used for each subsequent assessment. Scans should also be obtained as clinically indicated.

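### The test of Cycle 3 tumour-size change against PFS from enrolment uses a scan that can itself set PFS, so its p-value cannot show that early shrinkage predicts later outcome

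*SAP*

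**What the plan says.** The exploratory objective in SAP 4.3 is "To explore whether ongoing measurement of tumor shrinkage (such as changes in tumor size) correlate with efficacy measures". SAP 5.17.2 carries it out. It states "Tumor size is the sum of the tumor measurements for target lesions at each tumor evaluation", defines CTS as the change in that sum between baseline and the end of Cycle 3, divided by the baseline sum, and then says "The correlation between CTS and PFS will be tested using the" Spearman coefficient. It gives no significance level, does not say whether cohorts are pooled, and names no other method.

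The timing is set elsewhere. In SAP Table JTJH.5.2, note c says "radiologic imaging for tumor assessment will be performed approximately every 6 weeks (that is, every 3 cycles) starting at the end of Cycle 3". Protocol Table JTJH.2.2 agrees: "perform approximately every 6 weeks starting at the end of Cycle 3 (eg, Days 8-14").

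Under SAP 5.10.2, PFS starts at enrolment and ends at the first radiographic progression or at death. For the rest, "Patients known to be alive and without disease progression will be censored at the time of the last adequate tumor assessment". Note a of Table JTJH.5.2 adds "symptomatic progression that is not radiologically confirmed) will not be considered as tumor progression". In Protocol Table JTJH.2.3, the comment on the post-treatment scan reads "Not required if progressive disease is documented while on treatment or if there are clear signs of clinical progression".

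**The concern.** **Shared scan.** The scan that supplies CTS is also the first scheduled scan that can end PFS. A patient whose target lesions have grown enough to be called progression there receives one of the highest CTS values and one of the shortest PFS times from a single measurement. Some negative correlation is therefore built in by definition. A test against zero cannot separate that part from early shrinkage foretelling a longer time to progression afterwards.

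**Censoring (secondary).** PFS is censored, but ordinary Spearman has no event indicator and the SAP gives no other handling. Censoring unrelated to CTS mainly weakens the correlation. Censoring related to CTS can also distort the p-value, and the documents leave room for it. A patient with clear clinical progression need not be scanned again and is not counted as progressed. That patient is censored at the last adequate scan unless later progression, or death within two scan intervals, is recorded.

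**Stake.** If the result is read as prognostic, significance could mean only that some patients progressed at the scan that measured CTS.

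**Working it through.** **Does one scan feed both variables?** A cycle is 14 days, so without delays Days 8-14 of Cycle 3 are Days 28 + 8 = 36 to 28 + 14 = 42 of treatment, about week 6. Patients progressing there have PFS of about 6 weeks. Patients free of progression there next have a scheduled scan about 6 weeks later. Neither document sets a landmark, removes progressors at that scan or restarts the clock.

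**Is there a figure to reproduce?** No. The documents give no level, power or expected correlation for this test, so its behaviour has to be simulated on assumed inputs.

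**Set-up.**
- n = 58 (one cohort, Protocol 5.2); two-sided 5% test (assumed).
- CTS is standard normal. The top 0, 5, 10 or 20% of CTS values (0, 3, 6 or 12 patients) progress at the Cycle 3 scan.
- A random 0, 20 or 40% of the others also progress there for reasons unrelated to CTS.
- Everyone else progresses after an exponential time (mean 9 weeks) independent of CTS, detected at 6-weekly scans. Scan dates are spread by 3.5 days at the first scan and 7 days later, following the windows in Protocol Table JTJH.2.2.
- Of those with later scans, 0, 10 or 20% are censored at a scan before progression.

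CTS thus carries no information about anything after the scan.

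**Spearman rejection rates** (8,000 trials each; Monte Carlo standard error at 5% is √(0.05 × 0.95 / 8,000) = 0.0024):

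| Target-growth progression at Cycle 3 scan | No other progression there, no censoring | 20% other, 10% censored | 40% other, 20% censored |
|---|---|---|---|
| 0 | 0.054 | 0.049 | 0.051 |
| 3 (5%) | 0.171 | 0.113 | 0.077 |
| 6 (10%) | 0.574 | 0.331 | 0.168 |
| 12 (20%) | 1.000 | 0.863 | 0.506 |

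Down the rows, mean correlations are 0.00, -0.15, -0.28 and -0.49 in the first setting and 0.00, -0.08, -0.15 and -0.26 in the last. Changing the mean post-scan time to 6 or 15 weeks (10% growth, 20% other, 10% censored) gives 0.32 and 0.34. With both cohorts pooled (n = 116), the ranges at 5, 10 and 20% growth are 0.13-0.34, 0.34-0.91 and 0.80-1.00.

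**Landmark Cox test.** Using patients free of progression after the Cycle 3 scan, with time counted from it, rejection is 0.046-0.068 over the full grid (2,000 trials each).

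**Different assumptions.** A second simulation used CTS with SD 25 percentage points and mean from -25% to +10%, progression called at +20%, a 10-week median after the scan and no censoring. Spearman rejects in 14% of trials when 4% of patients progress at the scan, 63% at 12%, 96% at 21% and about 100% at 35%. A landmark rank correlation stays at 4.6-5.6%.

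**Censoring.** Unrelated censoring of 20%, without shared-scan progression, leaves Spearman at 5%. CTS-related censoring was simulated with no target-growth progression, 20% other-cause progression and 2,500 trials:

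| Odds ratio of censoring per SD of CTS | 1.0 | 1.5 | 2 | 3 |
|---|---|---|---|---|
| A: depends on CTS only, Spearman | 0.046 | 0.097 | 0.184 | 0.379 |
| A: landmark Cox | 0.057 | 0.052 | 0.050 | 0.065 |
| B: censored just before progression would be seen, Spearman | 0.048 | 0.063 | 0.092 | 0.138 |
| B: landmark Cox | 0.060 | 0.069 | 0.090 | 0.138 |

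The landmark repairs pattern A but not pattern B.

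**The case against.** The strongest reply is that the SAP promises only a correlation. SAP 4.3 and 5.17.2 mention neither prediction nor surrogacy, and the correlation from enrolment is a real one. Against the null of no correlation, most of the rejection rates above are power rather than false positives. This stands: the criticism applies only to a prognostic reading of the p-value.

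The size also depends on how many patients progress by target growth at the first scan, which the documents do not give. If none do, the test holds its level. This stands too, and is why only ranges are given.

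On censoring, the route visible in the documents, clinical progression without a scan, resembles pattern B, where Cox does no better than Spearman. Death within two scan intervals still counts as an event, and SAP 5.3 continues follow-up for recurrence and death after treatment stops; both narrow the route. So the case for a landmark rests mainly on the shared scan. Censoring is a reason to use a method with an event indicator and to report why patients were censored.

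A landmark also drops early progressors, who are part of the association the objective asks about. Keeping the whole-cohort coefficient as description answers that. The closing sentence of 5.17.2, which allows further exploratory analyses, permits a landmark analysis but does not commit to one.

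**Conclusion.** The concern holds. The overlap follows from the documents' own definitions of CTS, PFS and the scan schedule, and needs no assumption. Its size does rest on assumptions: for one cohort of 58, a nominal 5% test would reject in roughly 8-17%, 17-57% or 50-100% of trials when 5%, 10% or 20% of patients progress by target growth at the Cycle 3 scan, although CTS says nothing about later outcome.

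The consequence is limited. The analysis is exploratory and enters neither the ORR decision rules nor the futility rule, so the harm is a possible misreading of this one result. It is an improvement to consider, not an error that threatens the trial.

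**What to change.** In SAP 5.17.2:
- Make the inferential analysis a Cox model (or a censoring-aware concordance measure) of time from the Cycle 3 scan to progression or death, among patients alive and progression-free after that scan. Censor under Table JTJH.5.2 and enter CTS as a continuous covariate. SAP 5.17.1 already plans survival models for biomarkers against PFS and OS, so the model type fits, although that section sets no landmark.
- Keep the Spearman coefficient from enrolment as a description, without a p-value.
- Report the reasons for censoring, since a landmark does not cure CTS-related censoring that stands in for progression.
- State whether the analysis is per cohort or pooled.

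The cost is a few lines of SAP text and a short program; no new data are needed. The downside is precision and scope. Patients who progress or die at or before the Cycle 3 scan are excluded. In the simulated scenarios with target-growth progression, between 58 - 3 = 55 and (58 - 12) × 0.6 ≈ 28 of 58 remain, and the result speaks only to outcome after that scan.

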5.18. Clinical Trial Registry Analyses

Additional analyses will be performed for the purpose of fulfilling the Clinical Trial Registry (CTR) requirements.

Analyses provided for the CTR requirements include the following:

Summary of adverse events, provided as a dataset which will be converted to an XML file. Both Serious Adverse Events and 'Other' Adverse Events are summarized: by treatment group, by MedDRA preferred term.

- An adverse event is considered 'Serious' whether or not it is a TEAE.
- An adverse event is considered in the 'Other' category if it is both a TEAE and is not serious. For each Serious AE and 'Other' AE, for each term and treatment group, the following are provided:
 - the number of participants at risk of an event
 - the number of participants who experienced each event term
 - the number of events experienced.
- Consistent with www.ClinicalTrials.gov requirements, 'Other' AEs that occur in fewer than 5% of patients/subjects in every treatment group may not be included if a 5% threshold is chosen (5% is the minimum threshold).
- AE reporting is consistent with other document disclosures for example, the CSR, manuscripts, and so forth.

6. References

